With very few exceptions, most studies were characterized by high risk of bias in six bias domains (selection, performance, detection, attrition, reporting, other).¹⁴ Lack of randomization and blinding, and failure to explicitly define clinical outcomes contributed to these problems. The majority of studies used oral vitamin C supplementation. Oral doses, even those in excess of 200 mg, are associated with little or no clinically significant increases in circulating Vitamin C levels¹⁵, and pharmacokinetics of oral ascorbic acid dosing differs considerably from intravenous dosing.¹⁶ However most assessed studies reported positive effects of vitamin C supplementation. Meta-analysis of these papers indicated a significant overall reduction in both post-operative AF (9 studies; n= 1039 patients; odds ratio 0.37 [95% CI 0.28, 0.50]) and a small reduction in length of hospital stay (6 studies; n= 672 patients; mean difference -1.3 days [95% CI -1.6, -1.0]). A few papers reported measurements of isolated inflammatory and coagulation markers; however, results were equivocal. For example, vitamin C supplementation of CABG patients (usually in combination with various antioxidant cocktails) seemed to attenuate post-operative oxidative stress,¹⁷ myocardial “injury” (defined as a five-fold elevation of cardiac biomarker values and cardiac dysrhythmia),¹⁸ and endothelial dysfunction.¹⁹ In contrast, a study of cardiac surgery patients on or off CPB did not detect statistically significant differences between oral vitamin C and control groups in C-reactive protein (CRP) concentration, white blood cell (WBC) count, or fibrinogen concentration, markers of inflammation and coagulopathy.²⁰ However the study was underpowered because of early study termination, and data were uncorrected for non-normality, invalidating subsequent statistical analyses. In summary, although suggestive of benefit, current evidence of efficacy of high-dose vitamin C was of low quality with limited and/or irrelevant outcomes, necessitating development of more rigorous clinical trials.

SPECIFIC AIMS

Specific Aim 1: We will test the prediction that patients administered high-dose vitamin C will show clinically-significant reductions in pro-inflammatory and coagulation markers at peak response and at 48 hours relative to normal saline controls. Specifically, we will measure

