This is a two-arm trial comparing high-dose IV vitamin C to normal saline placebo controls (Fig. 1). Once informed consent is obtained, the time of surgery will be communicated to the VCU investigational pharmacy so that the medication can be appropriately prepared and delivered to the operating room. Prior to preparation, patients will be randomized to receive either control or Vitamin C solution. Randomization will be performed by a computer-generated permuted block design conducted by the investigational pharmacy. Both test and placebo preparations will be prepared by pharmaceutical staff in identical de-identified 50-mL medication bags so as to be indistinguishable by OR/ICU staff and investigators.

Vitamin C will be administered in doses of 200 mg/kg/day group divided into four doses per day at six hour intervals 48 hours. Patients randomized to the control (normal saline) group will receive equivalent fluid volume in identical dispensing bags; total study fluid volumes will be approximately 400 mL over the two-day study period. Blinded interventions will be administered in the OR by the anesthesiologist, and post-operatively by Cardiac Surgery ICU nursing staff and/or Cardiac Stepdown Units. All participating hospital units will be provided with thorough in-servicing. Nurses will be prompted to administer the medication via the patient-specific electronic medical record (EMR).

OUTCOMES

Enrollment Goals: (1) Up to 40 may be enrolled in order to reach completion of 24 out of 24 subjects to allow for withdrawals; (2) complete follow-up and follow-up data for 24/24 (100%) of enrolled subjects; (3) all patients (24/24) to receive study drug according to randomization designation; (4) all patients (24/24) to receive every scheduled dose of the study drug in a blinded manner; (5) all patients (24/24) to have coagulation and biolipid determinations performed for all.

Biomarker outcomes:

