- Those receiving insulin infusion or sliding scale insulin will have metabolic glucose screening on the schedule determined by the primary physician and paid for by the study
- Blood glucose monitoring for insulin administration guidance should *only* be by a metabolic laboratory measured blood glucose results, whether or not the study patient is receiving insulin
- To accommodate the required glucose monitoring via the metabolic lab, each subject will have a dedicated peripheral line
- Study personnel will follow each study patient closely to monitor insulin use to ensure that point of care glucose screening is suspended for the research subject.
- If subject loses central venous access (PICC line and arterial line acceptable), Vitamin C infusions are to stop but subject not withdrawn. Data will be collected through end of study.
- Point of care glucose testing may resume 36 hours after the last infusion of study drug.

ADVERSE EVENT REPORTING/SAFETY REPORTING

Investigators will determine daily if any clinical adverse experiences occur during the period from informed consent through study hour 48 and will be followed up through resolution, resolved with sequelae, unresolvable or death.

It is expected that diseases/illnesses/symptoms associated with the study population will occur in the study population, independent of investigation product exposure. These associated diseases/illnesses/symptoms will be considered as part of the study inclusion processes and/or study assessments and as such will not be considered 'reportable' Adverse Events (AE)/Serious Adverse Events (SAE) unless the Investigator has a reasonable doubt regarding the relatedness of the event to the investigational product.

The investigator will evaluate any changes in laboratory values and physical signs and will determine if the change is clinically important and different from what is expected in the course of treatment of the study patients. If clinically important and unexpected adverse experiences occur, they will be recorded on the adverse event case report form.

The following will be considered reportable adverse events:

For this trial, a *reportable adverse event* is defined as:

November 16, 2016

1. Any clinically important untoward medical occurrence in a patient receiving study drug or undergoing study procedures which is different from what is expected in the clinical course of a patient undergoing cardiac bypass surgery, or,

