- Unexpected, in terms of nature, severity, or frequency, given the research procedures that are described in the protocol-related documents, such as the IRB-approved research protocol and informed consent document; and the characteristics of the subject population being studied;

November 16, 2016

- Related or possibly related to participation in the research. In this guidance document, possibly related means there is a reasonable possibility that the incident, experience, or outcome may have been caused by the procedures involved in the research;
- Suggests that the research places subjects or others at a greater risk of harm (including physical, psychological, economic, or social harm) than was previously known or recognized.

WITHDRAWAL CRITERIA

The Principal Investigator may withdraw the subject at any time due to subject failure to adhere to protocol, or for safety concerns.

TRIAL MANAGEMENT

It is expected that the trial will terminate when the intended sample size (24 patients) has been achieved. However, the trial will be stopped prior to completion if: (1) the intervention is associated with adverse effects that call into question the safety of the test intervention; (2) problems with study recruitment or retention will significantly impact the ability to evaluate the study endpoints; (3) any new information that becomes available during the trial necessitates discontinuation of the trial.

The trial protocol and results will be published in peer-reviewed journals. All publications will follow the Consolidated Standards for Reporting Trials (CONSORT) statement [25]. Credit for the study will be assigned to collaborators who have actually performed designated work. The results of the trial will be reported first to trial collaborators. Summary outcome data and links to published data will be uploaded to the *ClinicalTrials.gov* website.

ETHICAL CONSIDERATIONS

This research will involve the use of fresh blood drawn from patients. The blood draws will be done, when possible, from in-dwelling arterial line and central line catheters. Additional venous blood draws from peripheral sites (e.g. antecubital, radial vein) may be required if the arterial and central line catheters have been removed before the conclusion of 48-hour study period, heparinized, or would be compromised by extra blood draws. Blood draw volumes will be approximately 20 mL.

The toxicity of Vitamin C is very low; therefore, potential benefit far outweighs known risks.

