Patients will not be paid for participation and there will be no penalties imposed for either refusal to participate or withdrawal of consent after enrollment.

Patient Drop-Out. Patients may refuse consent and leave the study at any time for any reason. This will be done by notifying the study physician or study coordinator. Subjects can be withdrawn from the study emergently by the attending study physician if they

November 16, 2016

develop signs and symptoms of adverse reactions.

DATA ANALYSES

Baseline demographic and clinical characteristics of study participants will be reported as descriptive summary statistics. Categorical variables will be reported as absolute and percent values. Continuous variables will be expressed as means and standard deviations, or median and interquartile ranges.

For each primary and secondary outcome, we will report the point estimate of effect and its precision (e.g. 95% confidence interval).

Biomarkers will be analyzed both individually and as clusters, or constellations, of variables. These clusters will be determined by exploratory factor analysis, discriminant analysis and/or vector analysis. Each cluster can be interpreted as a specific pathophysiological network process. The clusters can then be used as an empirical model to determine inter-dependencies between individual biomarkers. Discriminant function analysis is used to predict patient membership in either the Vitamin C treatment group or the control group by the entire suite of inflammation and coagulation variables (the predictor variables). Unlike cluster analysis, discriminant analysis is used when groups are known *a priori*. The measures of effect size are the *canonical correlation* (correlation between groups and the function), the *proportion of variance for each function*, calculated as $(\lambda_x/\Sigma\lambda_i)$ where λ_x is the eigenvalue for the function and $\Sigma\lambda_i$ is the sum of all eigenvalues, and *percent correctly classified*.³⁴ Finally vector analysis³⁵ can allow determination of the simultaneous directional change of all the measured inflammatory, biolipid and/or coagulation markers as a function of treatment group. These techniques allow a comparison of dynamic responses rather than a direct comparison of static levels which may not be particularly revealing of complex patterns of interactions between multiple variables.

No interim analyses will be performed because this trial is a small pilot.

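### The protocol lets patients with reactions be withdrawn and made up without stating a stop-drug-but-stay option, and leaves the denominator of the 24/24 goals unclear

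*Combined protocol and SAP*

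**What the plan says.** Three places deal with a patient who stops early.

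- **Ethical Considerations, Patient Drop-Out:** "Subjects can be withdrawn from the study emergently by the attending study physician if they" show signs of an adverse reaction.
- **Withdrawal Criteria:** "The Principal Investigator may withdraw the subject at any time due to subject failure to adhere to protocol, or for safety concerns".
- **Glucose Monitoring Plan**, on loss of central venous access: "Vitamin C infusions are to stop but subject not withdrawn. Data will be collected through end of study".

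The list of reasons for completing study drug (Study Design) has lost access and withdrawal from the study as separate entries. Its numbering skips item 2 in the supplied text, so a further drug-stop criterion may exist that cannot be read.

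Under Outcomes, Enrollment Goals:

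- Goal 1: "Up to 40 may be enrolled in order to reach completion of 24 out of 24 subjects to allow for withdrawals".
- Goal 2: "complete follow-up and follow-up data for 24/24 (100%) of enrolled subjects".
- Goal 4: "all patients (24/24) to receive every scheduled dose of the study drug in a blinded manner".
- Goals 3 and 5 (drug as randomised; assays performed) are likewise for all patients, 24/24.

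On timing, Intervention and Controls states: "Prior to preparation, patients will be randomized to receive either control or Vitamin C solution". Blood is drawn at baseline, about 60 minutes after protamine, and at 24 h and 48 h from baseline (each ±2 h). Urine is collected at baseline, 6 h and 24 h. Specific Aim 1 looks for "reductions in pro-inflammatory and coagulation markers at peak response and at 48 hours relative to normal saline controls". Data Analyses defines no analysis population.

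**The concern.** Randomisation comes before the drug is prepared, so any reaction to study drug happens after randomisation. Such reactions can depend on the arm. The protocol writes its data-preserving rule for a logistical stop (lost access) and not for the stop most likely to be related to treatment. If a patient with a reaction is withdrawn from the study and another is enrolled to reach 24, two things can follow.

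First, the remaining marker samples may not be taken. The marker comparison at 24 h and 48 h then moves towards one of selected completers, and 48 h is one of Aim 1's two comparison times.

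Second, the goal percentages may not reflect the event. Study Design makes performance metrics the success criteria because the sample is too small for hypothesis testing, and Future Research names poor retention as a ground for not going on to the main trial. A retention or dosing figure whose denominator is open is therefore a weakness in a main product of the pilot.

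Non-adherence is the lesser part of this, since staff give the infusions.

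**Working it through.** **Inputs.** Target 24, 12 per arm (Study Design). Ceiling 40, goals at 24/24 (Enrollment Goals). Draw times and windows (Post-Randomization Treatment). The documents give no withdrawal rate.

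**The plan's own figures.** 12 × 2 = 24. The ceiling leaves room for 40 − 24 = 16 non-completers, or 16/40 = 40% of those enrolled. This is an upper limit, not a forecast, and some of the 16 could be lost before randomisation.

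**1. Denominator of the goals.** Let k be the number withdrawn after randomisation and made up. On completers the goal is always 24/24. On all randomised it is 24/(24 + k), taking those withdrawn as not meeting the goal. Intervals are exact (Clopper-Pearson) 95%.

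| k | On completers | On all randomised |
|---|---|---|
| 0 | 24/24 = 100% (85.8–100) | 24/24 = 100% (85.8–100) |
| 1 | 24/24 = 100% (85.8–100) | 24/25 = 96.0% (79.6–99.9) |
| 2 | 24/24 = 100% (85.8–100) | 24/26 = 92.3% (74.9–99.1) |
| 4 | 24/24 = 100% (85.8–100) | 24/28 = 85.7% (67.3–96.0) |

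**2. Two early stops under goal 4 (every dose given).** A patient who loses access is kept, so on a plain reading counts as a miss: 23/24 = 95.8% (78.9–99.9). A patient withdrawn for a reaction and made up leaves 24/24, if the goal is counted on completers.

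**3. Which wording sets the denominator.** Goal 2 refers to enrolled subjects but fixes the count at 24; goal 1 allows 40 to be enrolled. Both cannot hold once anyone is made up, so the text does not settle whether 24 means completers or everyone enrolled.

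**4. Samples at risk.** The windows are 22–26 h and 46–50 h. Withdrawal after the second draw and before hour 22 may lose 2 of the 3 post-baseline blood draws. If the 6 h urine has been collected, it may also lose 1 of the 2 post-baseline urines. Withdrawal between hours 26 and 46 may lose the 48 h draw.

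**5. Chance that it arises at all.** The rate p per patient is an assumption. The chance of at least one withdrawal is 1 − (1 − p)^n.

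| Assumed p | All 24 patients at risk | Only the 12 on vitamin C at risk |
|---|---|---|
| 1% | 21% | 11% |
| 5% | 71% | 46% |

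**The case against.** The strongest reply is that nobody would be blind to withdrawals. Needing 28 patients to reach 24 completers is itself visible under goal 1. Study Design lists retention and study flow among the performance criteria, Trial Management makes retention problems a stopping condition, and publications are to follow CONSORT. Goal 2's mention of enrolled subjects also resists a completers-only count. All of this stands. A reader might infer that the goals cannot show early stops; the documents do not support that. What remains is that none of these provisions fixes the denominator of the goal percentages.

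Withdrawal is also discretionary: both clauses are permissive, and nothing forbids stopping the drug while keeping the patient. Discretion after a safety event is defensible where a fixed rule suits a logistical one. That stands too. Because item 2 of the drug-stop list cannot be read, one should not infer that the plan has no drug-stop rule for reactions. The point is only that the two withdrawal clauses do not state the option.

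Finally, a reader might infer that sampling ends at withdrawal or that earlier samples are thrown away. No section says either. The protocol's follow-up to discharge and its follow-up of adverse events favour continued chart and safety data. They do not mention the study draws, so loss of the 24 h and 48 h samples is a risk that arises from silence, not a stated rule. The protocol also reports that few side effects are known, and dosing lasts only 48 hours.

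**Conclusion.** The point holds as a minor one. The withdrawal clauses do not carry over the stay-in rule that the protocol already uses for lost access, and the 24/24 goals have an ambiguous denominator once withdrawals are made up. On a completers-only reading, two made-up withdrawals would separate a reported 100% from 92.3% of all randomised; one would separate it from 96.0%.

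This rests on three conditions: a reaction occurs after randomisation, the physician chooses full withdrawal over stopping the drug, and the patient is made up. The loss of marker samples further assumes that study draws stop at withdrawal. The protocol permits each of these and requires none. The frequency of such withdrawals, and the direction and size of any bias in the marker comparison, cannot be estimated from the documents. The 1% to 5% rates above only illustrate the range.

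**What to change.** 1. In Withdrawal Criteria and Patient Drop-Out, make stopping study drug the default response, and extend the Glucose Monitoring Plan's rule ("Vitamin C infusions are to stop but subject not withdrawn. Data will be collected through end of study") to every early drug stop. Leave the physician free to omit any draw or procedure for safety. Keep full withdrawal for withdrawn consent or where taking part is itself unsafe. Chart outcomes and safety follow-up continue unless consent is withdrawn.
2. Report goals 2 to 5 out of all randomised patients as well as out of the 24 completers, and include all randomised patients with available samples in the biomarker comparison.

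**Cost.** One sentence in each of the two clauses and one extra denominator in the report. For an affected patient, typically up to two further blood draws of about 20 mL and one 5 mL urine sample. Partly treated patients will dilute the effect estimate slightly, and the feasibility percentages may look less favourable.

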- a) Levels of circulating pro-inflammatory biomarkers profiles (CRP, IL-6, TNF- α), NGAL (in urine), and lipid pro- and anti-inflammatory mediators (in plasma);
- b) Levels of coagulation biomarker and platelet function (e.g. fibrinogen, platelet counts, thrombomodulin, R, K, MA, G, angle, LYO)

Specific Aim 2: We will test the prediction that reduced post-surgical inflammatory burden of patients administered high-dose vitamin C will result in clinically significant reductions in hospital-based outcomes (such as length of hospital stay, length of ICU stay.)

STUDY DESIGN

This is a prospective, double-blind, placebo-controlled, randomized pilot trial comparing high-dose intravenous vitamin C to placebo (normal saline) infusions in elective non-emergent cardiac bypass patients. Double blinding will be used at enrollment, randomization, and throughout treatment, sampling, analysis, and data interpretation phases.

The purpose of this pilot study is to demonstrate **performance feasibility** and **proof of concept (PoC)** before initiation of a full-fledged clinical trial. Both financial and personnel constraints limit the total patient enrollment to 24 (12 per arm). Because sample sizes are so small, hypothesis testing cannot be a central feature of this proposal. Instead, success criteria will consist of tangible and measurable performance metrics relating to trial performance and PoC. *Performance success criteria* relate to the logistics and processes involved in the execution of the study itself (e.g. recruitment, retention, study flow, operations, management, obtaining samples, sample processing, documentation, compliance oversight). *Proof of concept* will be determined by large effect size differences (20%) between test and experimental intervention groups in one or more of the key inflammation and coagulation markers (see **OUTCOMES**).

It is unethical to consider running a phase III trial without sufficient data or feasibility information. This pilot trial will be extremely useful to inform the planning and execution of the future large-scale trial, especially with respect to feasibility and sample size calculations. Proof of concept information will be essential for writing major grants, which usually require such preliminary information for assessing scientific validity²¹⁻²³

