Exclusion criteria are: (1) known allergy to Vitamin C; (2) pregnant or breastfeeding; (3) prisoner; (4) emergent cardiac surgery patients; (5) scheduled for single CABG procedure; (6) low ejection fraction ($< 35\%$); (7) current autoimmune disease or on immunosuppressant therapy, including prednisone, prednisolone, dexamethasone, mycophenolate, tacrolimus, cyclosporine, or azathioprine; (8) presence of renal calculi, or renal dysfunction (pre-operative creatinine clearance < 40 , or serum creatinine greater than 1.8 mg/dl); (9) known bleeding diathesis such as hemophilia, Von Willebrand's disease, or liver failure, or receiving concurrent anticoagulant therapy (such as warfarin, dabigatran or apixaban) for venous or arterial thrombosis; (10) active infection or tumor; (11) prior history of atrial fibrillation (AF); (12) known diagnosis of diabetes mellitus, or preoperative (this surgery) A1C test result ≥ 6.5 ; (13) diagnosed with diabetic ketoacidosis

November 16, 2016

(DKA); (14) known coagulopathy prior to surgery (INR > 1.5).

Patient numbers/sample size: This is a feasibility/ proof of concept pilot trial; therefore power calculations are not appropriate. Patient enrollment numbers are limited *a priori* by the funding available for this project and costs inherent to enrollment, randomization and blinding procedures, sampling, and sample processing.

Consent Procedures. All eligible patients will be approached prior to their scheduled surgery by the study coordinator or attending surgeon. A formal Institutional Review Board (IRB)-approved Informed Consent form will be discussed with the patient, and all questions answered prior to obtaining informed patient consent in writing. Informed consent will be documented in the patient medical record, and the clinical research office and each enrolled patient will receive a copy of his/her signed consent form.

INTERVENTION AND CONTROLS

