Our targeted lipidomic analysis will examine a specific subset of lipids identified alterations in the arachidonic acid metabolite pathway associated with inflammation and coagulopathy. We will track patient condition before, during, and after CPB by mass spectrometric profiles of selected biolipids with the initial focus on free fatty acids, eicosanoids, 3-PUFA-derived lipid mediators, phospholipid substrates of cPLA2 α (including oxidized forms), and isoprostanes, which are well-characterized markers of oxidative stress and redox status. Lipid entities will be quantitatively determined via LC tandem mass spectrometry.²⁸⁻³⁰

Clinical outcomes: Clinical data will be obtained from the patient's chart under direct supervision of the PI by a research coordinator and/or a graduate student listed in the study personnel. Data will include: (1) Demographics (age, race, ethnicity, gender, height, weight); (2) Pertinent medical history (hypertension, congestive heart failure); (3) Surgery data (cardiac surgeon, date and time of surgery, time and details of bypass, total heparin administered, total protamine administered, blood products administered (type, units),

November 16, 2016

other concomitant medications [times, dosages/amounts]); (4) Surgical complications (e.g. fever, respiratory failure, intubation (Y/N, duration), chest tube drainage amount); (5) Incidence of AF; (6) Hospital outcomes: length of ICU stay, length of step-down and/or floor stay, and patient discharge disposition. Patients will be followed up through hospital discharge or in-hospital death.

POST-RANDOMIZATION TREATMENT

All clinically-indicated treatments (including blood product, medications, and fluid administration) will be given as appropriate per attending physician discretion.

Study-specific blood samples will be obtained by the anesthesiologist or nursing staff, depending on the patient's location at each time point, at four times:

- 1st Draw: Baseline (after anesthesia induction but prior to drug administration)
- 2nd Draw: Approx. 60 min. after protamine sulfate is administered (during CPB),
- 3rd Draw: 24 hours post-baseline (+/- 2 hours),
- 4th Draw: 48 hours post-baseline (+/- 2 hours).

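### The baseline samples have no stated role in the individual biomarker estimates, and the 20% proof-of-concept criterion has no stated scale

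*Combined protocol and SAP*

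**What the plan says.** - **Estimates.** DATA ANALYSES promises, for every primary and secondary outcome, that "we will report the point estimate of effect and its precision (e.g. 95% confidence interval"). It says biomarkers will be analysed singly and in clusters. For a single marker it names no model, covariate, transformation or way of handling the repeated draws.
- **Baseline data.** POST-RANDOMIZATION TREATMENT lists a "1st Draw: Baseline (after anesthesia induction but prior to drug administration"), then draws about an hour after protamine, at 24 hours, and finally the "4th Draw: 48 hours post-baseline (+/- 2 hours"). Urine is also taken at baseline, 6 hours and 24 hours.
- **Aim and criterion.** Specific Aim 1 predicts "clinically-significant reductions in pro-inflammatory and coagulation markers at peak response and at 48 hours relative to normal saline controls". STUDY DESIGN says proof of concept will be "determined by large effect size differences (20%) between test and experimental intervention groups" in at least one key marker. Neither gives an estimator or a scale.
- **Size and purpose.** STUDY DESIGN says "constraints limit the total patient enrollment to 24 (12 per arm"). The study population section adds "This is a feasibility/ proof of concept pilot trial; therefore power calculations are not appropriate". The results are meant to inform the sample size of the later trial.
- **Non-normality.** LITERATURE SEARCH faults an earlier study of CRP, white cell count and fibrinogen because "data were uncorrected for non-normality, invalidating subsequent statistical analyses". The same markers are measured here, and the plan gives no rule for non-normality.

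**The concern.** In a trial this small, the baseline samples are the cheapest source of precision, and they are already being collected. Randomising 12 per arm leaves sizeable chance imbalances. Where a marker's baseline predicts its later value, part of that imbalance enters an unadjusted follow-up comparison.

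The 20% criterion decides whether the concept is judged proven. It can be read from arithmetic means, medians, geometric means, change scores or baseline-adjusted values, and these can disagree in the same data. A later sample-size calculation also needs a defined estimator with a matching variance.

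**Working it through.** **Figures in the plan.** The sample size comes from funding and the documents give no SD, so there is no power calculation to reproduce: 24/2 = 12 per arm.

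**Inputs.** From the documents: 12 per arm, 95% intervals, one baseline value per marker, and the 20% criterion. Assumed, because the documents are silent: lognormal markers, coefficient of variation (CV) 0.3 to 1.0, and baseline to follow-up correlation r = 0 to 0.7.

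**Step 1: width with ANCOVA relative to follow-up alone.**

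- Follow-up alone: t(0.975, 22) × SD × √(2/12), with t = 2.074.
- ANCOVA: t(0.975, 21) × SD × √(1 − r²) × √(2/12) × √(1 + 1/20), with t = 2.080. The last factor is the average cost of chance baseline imbalance.
- Ratio: (2.0796/2.0739) × √1.05 × √(1 − r²) = 1.0275 × √(1 − r²).
- Change score relative to follow-up alone: √(2(1 − r)).

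| r | ANCOVA | Change score |
|---|---|---|
| 0 | 1.03 | 1.41 |
| 0.3 | 0.98 | 1.18 |
| 0.5 | 0.89 | 1.00 |
| 0.7 | 0.73 | 0.77 |

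ANCOVA breaks even where 1 − r² = 1/1.0275² = 0.947, so at r of about 0.23. Squaring the widths gives a variance cut of about 21% at r = 0.5 (0.890² = 0.79) and 46% at r = 0.7 (0.734² = 0.54). Simulation of 20,000 trials per setting gave the same width ratios.

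**Step 2: what this does to an interval.** At CV 0.5 the log SD is √ln(1.25) = 0.472, so the unadjusted log half-width is 2.074 × 0.472 × 0.408 = 0.400. For an observed ratio of 0.80 the 95% interval is:

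- follow-up alone: 0.54 to 1.19
- ANCOVA, r = 0.3: 0.54 to 1.18
- ANCOVA, r = 0.5: 0.56 to 1.14
- ANCOVA, r = 0.7: 0.60 to 1.07

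**Step 3: chance imbalance.** At CV 0.5 the between-arm difference in mean log baseline has standard deviation 0.472 × 0.408 = 0.193. With equal SDs, a fraction r of it carries into the follow-up comparison. At r = 0.5, a one-SD imbalance shifts the log ratio by 0.096. That alone can give a ratio of exp(−0.096) = 0.91, nearly half of the 20% criterion.

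**Step 4: the criterion with no true effect.** Simulation of 40,000 null trials per setting gave the chance that one marker at one time point shows a reduction of at least 20%. At CV 0.5, geometric means of follow-up values give about 12.5%. ANCOVA on logs gives about 12% at r = 0.3, 10% at r = 0.5 and 6% at r = 0.7.

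The open choice matters more. At CV 0.5 and r = 0.5, at least one of five readings (raw means, medians, log follow-up, log change, log ANCOVA) meets the criterion in 28% of null trials. In 25% of trials the five readings disagree.

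**Step 5: does the raw scale break the interval?** No. Simulated coverage of the raw-mean 95% interval was 95 to 96% up to CV 1.0.

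**The case against.** **Silence is not a decision.** A reader might infer that the plan commits to unadjusted arithmetic means of skewed markers. It does not. DATA ANALYSES allows medians with interquartile ranges, names no effect estimator, and prefers dynamic responses over static levels for its multivariate techniques. The documents give no marker distributions for this trial, so skewness is plausible but assumed. This stands. What remains is that no single-marker model or change formula is given.

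**The gain depends on an unknown correlation.** Baseline is drawn before surgery and the later draws follow bypass, so r may be low for some markers. At r = 0.3 the gain is 2%, and at r = 0 there is a 3% loss. One cannot say in general that the intervals will be wider than the data allow. This also stands, though a 3% cost is small beside a possible 11 to 27% gain.

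**The log scale adds little by itself.** Power for a ratio of 0.80 is about 20% on logs against 18% on raw means at CV 0.5, and 10% against 7% at CV 1.0. A reader might take the protocol's criticism of the earlier study to mean that raw-scale intervals here would be invalid. The coverage result does not support that. Nor does a 20% difference have to be a ratio of geometric means. The log scale is a sensible choice that needs stating.

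**It is a pilot without hypothesis testing.** True, and adjustment does not rescue the criterion: at CV 0.5 the interval around 0.80 still includes 1 at r = 0.7. But the plan promises estimates with precision and adopts a numerical criterion, and both need a defined estimator.

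**Conclusion.** The point holds as a gap in specification for which a better method is available at almost no cost. The individual biomarker estimates make no stated use of the baseline samples, and the 20% criterion has no scale.

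Baseline adjustment is close to neutral for r up to about 0.3 and worthwhile from about 0.5. A change score, the obvious informal alternative, would do harm at low r. These relative widths depend only on 12 per arm and the assumed r. The intervals around 0.80 and the null probabilities also assume lognormal markers with the stated CVs.

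The matter should be settled before unblinding. It affects precision and the reading of proof of concept. The conduct of the trial and the validity of a correctly computed interval are not in question.

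**What to change.** Add to DATA ANALYSES:

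> Each individual marker will be analysed at each post-baseline sample by ANCOVA (or one repeated-measures model) with arm and the baseline value as covariates. Positive concentration markers (e.g. CRP, IL-6, TNF-alpha, thrombomodulin, lipid mediators, urine NGAL) will be log-transformed and reported as baseline-adjusted ratios of geometric means with 95% CI, and the 20% criterion will be read on that ratio. Viscoelastic parameters will be analysed on their original scale with baseline adjustment. Values below the detection limit will be handled by one prespecified rule.

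The separate treatment of viscoelastic parameters is deliberate, because a log scale need not suit an angle or a lysis measure that can be zero. The detection-limit rule is needed because LIMITATIONS OF PROPOSED RESEARCH itself foresees lipid concentrations too low to measure.

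Cost: a paragraph of text, minor programming, one degree of freedom per model (22 to 21), and intervals about 3% wider for any marker whose baseline is uncorrelated with follow-up. No extra samples or patients are needed.
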